7.6 Endpoints, Safety Outcomes and Other Parameters

7.6.1.Primary Endpoints

Primary Patency Rate

In order to mitigate the challenges with DUS interpretation, clinical validation through independent noninvasive core laboratory and/or angiography will be performed in order to correctly validate and definitively assess percent diameter stenosis. DUS is highly reliable in identifying widely patent stents – however, correlation studies of DUS with angiography have confirmed that DUS is not as accurate when results suggest a stenosis. To lessen the risk of inaccurate readings, if a stenosis is detected in DUS (RAS > 60%) or if the DUS is non-diagnostic due to an imaging quality problem then a contrast angiogram will be used to assess the degree of restenosis of the covered stent(s) at the 9-month visit (± 30 days).

The primary efficacy variable is the primary patency rate, defined as continuous patency without the occurrence of a total occlusion (complete obstruction or a closure of a passageway or vessel determined by DUS or contrast angiogram) of the original lesion, and

Amendment #1: 15Jul13

Confidential

- without a re-intervention due to a clinically driven restenosis or occlusion to treat a partial or total occlusion of the stented segment,
- or bypass of the stented segment due to clinically-driven restenosis or occlusion

The primary patency will be calculated on a per lesion basis – for purpose of analysis in cases in which multiple lesions are covered by one stent then the stented segment will be considered as one lesion. The cumulative incidence of patency at 9 months will be computed as the number of lesions that met primary patency divided by the number of subject-lesions for the population being analyzed.

Change from Baseline in Systolic Blood Pressure

Systolic blood pressure will be assessed at each follow-up study visit. Blood pressure measurements will be obtained with a certified, calibrated, and validated equipment. Subjects will be instructed to refrain from exercise, smoking or caffeine ingestion for 30 minutes before blood pressure measurement, and measurements will be obtained after at least 5 minutes of rest. At each time point, a minimum of three (3) readings separated by 2 minutes will be averaged.

The primary clinical outcome is the improvement in systolic blood pressure (SBP) at 9-months as compared to baseline systolic blood pressure computed as follows:

$$\text{SBP change from baseline} = (\text{SBP value at 9-months} - \text{SBP value at baseline})$$

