## **2.2 CO-PRIMARY ENDPOINTS**

### Functional Endpoint

Assessment of primary patency rate at 9-months, defined as continuous patency without the occurrence of a total occlusion of the original lesion, without a re-intervention to treat a partial or total occlusion of the stented segment, or bypass of the stented segment due to clinically-driven restenosis or occlusion.

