- 4) To evaluate TLR measured as the proportion of subjects that require a clinically-driven re-intervention of the target lesion through 9-months.
 - i) A clinically-driven TLR is defined as a TLR (PTA, bare metal stent or repeat covered stent deployment, or surgical bypass) due to documented recurrent hypertension from 30-days post-procedure level and/or deterioration in renal function from baseline value, associated with angiographic core laboratory adjudication of a \geq 60% diameter covered stent restenosis.

Clinically driven TLR were reviewed and adjudicated by the Clinical Event Committee.

- 5) To determine the rate of incidental TLR defined as rate of TLRs not meeting the definition of a clinically driven TLR.

Amendment #1: 15Jul13

- 6) To measure improvement in SBP control assessed at 30-days, 9-months, 12-months, 24-months and 36-months.
- 7) To determine the secondary patency rate at 9-months after a clinically-driven TLR; which restores patency after total occlusion.
- 8) To measure the change in number and dosage of anti-hypertensive medications as compared to baseline.
- 9) To evaluate renal function compared to baseline as measured by estimated Glomerular Filtration Rate (eGFR) at 30-days and 9-months.

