6.2 Changes from the Analyses Planned in the Protocol/CIP

Due to the early termination of enrollment for Protocol/CIP No. iCAST™ RX-ARAS-001, all inferential analysis should be interpreted as descriptive and will be carried out in an exploratory manner.

The following changes were applied:

1. Missing data will not be imputed.
2. Sensitivity analysis will be limited to evaluating the primary analysis results using the per protocol population.
3. Supportive analysis of the revascularization information using a time to event approach will be performed.

Confidential

7. BASELINE, EFFICACY and SAFETY EVALUATIONS

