A clinically-driven TLR is defined as a target lesion revascularization (PTA, bare metal stent or repeat covered stent deployment, or surgical bypass) due to documented recurrent hypertension from 30-days post-procedure level and/or deterioration in renal function from baseline value, and associated with angiographic core laboratory adjudication of a $\geq 60\%$ diameter covered stent restenosis.

The percentage of TLRs will be derived as the number of subject-lesions that require a clinically-driven re-intervention divided by the number of subject-lesions in the ITT population.

5. Rate of incidental TLR

The rate of TLRs not meeting the definition of a clinically-driven TLR will be derived as the number of observed non-clinically driven TLRs divided by the total number of subject-lesions in the ITT population.

6. Improved SBP control assessed at 30-days, 9-months, 12-months, 24-months and 36-months.

The change from baseline in systolic blood pressure (SBP) at each follow-up time point will be computed as follows:

$$\text{SBP change from baseline} = (\text{SBP value at follow-up} - \text{SBP value at baseline})$$

7. Secondary patency rate at 9-months

Secondary patency rate at 9-months after a clinically-driven TLR which restores patency after total occlusion. For each subject-lesion, an indicator variable will be derived which identifies if the lesion meets secondary patency. The incidence of secondary of patency at 9 months will be computed as the number of subject-lesions that met secondary patency divided by the number of subject-lesions for the ITT population.

Confidential

8. Change in number and dosage of anti-hypertensive medications

Anti-hypertensive medications as well as the dosage will be recorded at baseline and throughout the study follow-up. The total number of anti-hypertensive medications will be computed as the sum of all available anti-hypertensive medications at each time point. Change from baseline will be computed as follows:

Change from baseline in the number of antihypertensive medications = (number of anti-hypertensive medications at follow-up – the number of anti-hypertensive medications at baseline)

Additionally, an indicator variable which detects if an increase in the number of antihypertensive medications (change from baseline > 0) was observed will be derived.

Similarly, the change from baseline in the anti-hypertensive medication dosage (within the same medication) will be computed as follows:

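### The SAP adds a clinically driven condition to the re-intervention component of primary patency, does not list it as a change, and can only raise the rate or leave it unchanged

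*SAP*

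**What the plan says.** The protocol gives one definition of primary patency in four places: the Protocol Summary, 2.2, 5.1 and Appendix 2. After excluding total occlusion of the lesion, it requires that there be no "re-intervention to treat a partial or total occlusion of the stented segment, or bypass of the stented segment due to clinically-driven restenosis or occlusion". The clinically driven condition appears once, at the end, after bypass.

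SAP 7.6.1 splits this into bullets. The first reads "without a re-intervention due to a clinically driven restenosis or occlusion to treat a partial or total occlusion of the stented segment". The second reads "or bypass of the stented segment due to clinically-driven restenosis or occlusion". The condition now stands on both components. Total occlusion, seen on ultrasound or contrast angiogram, remains a failure with no clinical condition attached.

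SAP 6.2 introduces its list with "The following changes were applied" and gives three items: no imputation of missing data, sensitivity analysis confined to the per-protocol population, and a time-to-event analysis of revascularization. SAP section 2 covers descriptive inference and missing data. Neither mentions the patency definition.

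Both documents expect some re-interventions that are not clinically driven. One SAP objective is "To determine the rate of incidental TLR defined as rate of TLRs not meeting the definition of a clinically driven TLR".

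**The concern.** A clinically driven target lesion revascularization (TLR) must be "due to documented recurrent hypertension from 30-days post-procedure level and/or deterioration in renal function from baseline value", with core-laboratory restenosis of at least 60%. A restenosed stent that is re-treated without either clinical trigger is an incidental TLR. If the stent was only partly occluded, the protocol counts a patency failure and the SAP counts a success.

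Such cases are foreseeable. Duplex ultrasound is scheduled at 30 days and 9 months, and a 9-month finding of 60% or more leads to angiography, so restenosis can come to light in a subject with stable blood pressure and renal function.

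At stake is the meaning of the reported patency rate. The goal of 70% rests on published restenosis rates and has not moved, while the endpoint compared with it has become easier to meet. The only planned sensitivity analysis changes the population, not the definition, so it would not show the effect.

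**Working it through.** **1. The plan's own figure.** Inputs from Protocol 5.1 and 5.2: null rate 0.70, assumed rate 0.82, exact binomial test, one-sided level 0.025, 125 evaluable, at most 27 failures. With X ~ Bin(125, p) and a pass at X ≥ 98:
- P(X ≥ 98 | 0.70) = 0.0230
- P(X ≥ 98 | 0.82) = 0.876

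The stated 87% power and 27 failures reproduce.

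**2. Which lesions change status.**

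| Event in the lesion | Protocol | SAP 7.6.1 |
|---|---|---|
| Total occlusion, any trigger | Failure | Failure |
| Clinically driven re-intervention | Failure | Failure |
| Clinically driven bypass | Failure | Failure |
| Incidental re-intervention for partial occlusion, no other failure | Failure | Patent |

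Only the last row differs, and it moves in one direction.

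**3. Size per lesion.** Enrolment stopped at 68 subjects (SAP 6.1). The lesion count is not given. Applying the 1.2 lesions per subject that both documents quote from another renal trial gives 68 × 1.2 = 81.6, about 82 (assumption). Each reclassified lesion adds 1/82 = 1.2 points. At the planned 125 units it would add 1/125 = 0.8 points.

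**4. Effect on the comparison with 70%.** Let d be the share of lesions whose only failure is an incidental re-intervention. Under the SAP definition the true rate is the protocol rate plus d. The documents give no value for d, so 0, 2 and 5 points are assumptions. At 82 lesions, 2 points is about 1.6 lesions and 5 points about 4.1. The chance of passing is P(X ≥ r | n, 0.70 + d), where r is the smallest count significant at 0.025:

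| Units n | r | Most failures allowed | d = 0 | d = 2 points | d = 5 points |
|---|---|---|---|---|---|
| 82 (68 × 1.2) | 66 | 16 | 2.2% | 5.2% | 15% |
| 68 (one lesion each) | 56 | 12 | 1.5% | 3.4% | 10% |
| 125 (planned) | 98 | 27 | 2.3% | 6.5% | 22% |

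With a true protocol rate of 0.75 and 82 lesions, the chances are 15%, 27% and 52%.

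**The case against.** **The protocol sentence can be read another way.** Its closing phrase could govern both re-intervention and bypass, in which case the SAP merely clarifies. Protocol 2.3 lends some support, since it treats angioplasty, stenting and bypass alike when defining clinically driven TLR. The comma and the position of the phrase favour the narrower scope, and the SAP had to insert the words to obtain the other reading. The ambiguity is real, but it is a reason to settle the wording openly. Clinically driven restenosis is also not defined as a term; only clinically driven TLR is.

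**The effect may be nil.** If no otherwise patent lesion has an incidental re-intervention by 9 months, the two rates are identical. This stands.

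**Inference is now descriptive, and the events stay visible.** SAP sections 2, 6.2 and 8.7 withdraw confirmatory inference. The incidental TLR rate is reported, and SAP 9.11.11 lists revascularizations by lesion with their indication. This lowers the severity. It does not remove the point: SAP 9.9 keeps p < 0.025 as significant, 9.9.1 keeps the 70% comparison, and a reader should not have to rebuild the protocol's primary rate from listings.

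**Two stronger readings are tempting.** A reader might set the 21.4% restenosis average (Protocol Table 3) against the 8.5% TLR average (Table 4) and take that gap as the effect of the edit. The documents do not support this. The protocol definition does not count untreated restenosis as failure either, so the gap between an event-based endpoint and an imaging-based goal predates the SAP wording and would survive its correction. Nor does Table 4 say that its TLRs were clinically driven. A reader might also infer that the endpoint was redefined after enrolment ended. The present SAP text does postdate the November 2017 stop, but no other SAP is available, so the date of the insertion cannot be shown.

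**Conclusion.** The discrepancy is real and unlisted, and it favours the device whenever it has any effect. It is confined to one component of the definition and one class of lesion. The size is unknown: 1.2 points per reclassified lesion at an assumed 82 lesions, with the chance of passing at a true protocol rate of 70% going from 2.2% to 5.2% or 15% under assumed shares of 2 or 5 points. These chances treat lesions as independent and use the retained 0.025 threshold. Because inference is descriptive, they show how far the reported comparison could shift; they are not confirmatory error rates. The conclusion also rests on reading the protocol's qualifier as attached to bypass alone. The point should be fixed, but it does not by itself undermine the plan.

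**What to change.** In SAP 7.6.1, define the primary rate as the protocol does: any re-intervention on the stented segment for partial or total occlusion is a failure. State explicitly that the clinically driven qualifier applies to bypass only. List the narrower version in SAP 6.2 as a supportive analysis, and report both rates side by side. The incidental TLR data needed are already collected for secondary endpoint 5.

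The cost is a few lines of SAP text, one extra row in the patency table, and a primary rate that may be slightly less favourable. The planned sample size is unaffected.

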7.6.2. Secondary Endpoints

The secondary endpoints are:

1. The occurrence of procedure-related major adverse events (MAEs)

For each subject, an indicator variable which identifies if a MAE was observed will be defined. The incidence of MAE occurrence will be computed as the number of subjects with a reported MAE divided by the number of subjects in the Intent-to-treat (ITT) population.

Confidential

MAEs include:

- a. Procedure-or device-related occurrence of death
- b. Q-Wave MI
- c. Clinically driven TLR
 - i. Defined as a TLR (PTA, bare metal stent or repeat covered stent deployment, or surgical bypass) due to documented recurrent hypertension from 30-days post-procedure level and/or deterioration in renal function from baseline value, associated with angiographic core laboratory adjudication of a $\geq 60\%$ diameter covered stent restenosis.
- d. Significant embolic events
 - i. Defined as unanticipated kidney/bowel infarct clinically driven by symptoms of abdominal or back pain and confirmed with CT scan or open surgery, lower extremity ulceration or gangrene, or kidney failure after 30-days, 9-months, 12-months, 24-months, and 36-months.

2. Technical device delivery/deployment success

For each subject-lesion, the percent of residual stenosis will be measured via QVA by an independent core laboratory. An indicator variable that classifies success or failure of the delivery and deployment will be derived and computed as follows:

- Technical stent delivery will be defined as a success ("1") if the residual angiographic stenosis is less or equal to 30% after covered stent deployment. Otherwise, it will be defined as a failure ("0"). The percentage of subject-lesions with successful technical stent delivery/deployment will be computed by dividing the number of delivery/deployment successes by the number of subject-lesions in the ITT population.

3. Acute procedural success

For each subject-lesion, the procedural success will be derived as a composite outcome of observing technical success in the absence of a MAE prior to hospital discharge. The proportion of subject-lesions with acute procedural success will be computed as the number of subject-

Amendment #1: 15Jul13

Confidential

lesions with technical success in the absence of a MAE divided by the total number of subject-lesions in the ITT population.

4. Target lesion revascularization (TLR)

A clinically-driven TLR is defined as a target lesion revascularization (PTA, bare metal stent or repeat covered stent deployment, or surgical bypass) due to documented recurrent hypertension from 30-days post-procedure level and/or deterioration in renal function from baseline value, and associated with angiographic core laboratory adjudication of a $\geq 60\%$ diameter covered stent restenosis.

The percentage of TLRs will be derived as the number of subject-lesions that require a clinically-driven re-intervention divided by the number of subject-lesions in the ITT population.

5. Rate of incidental TLR

The rate of TLRs not meeting the definition of a clinically-driven TLR will be derived as the number of observed non-clinically driven TLRs divided by the total number of subject-lesions in the ITT population.

6. Improved SBP control assessed at 30-days, 9-months, 12-months, 24-months and 36-months.

The change from baseline in systolic blood pressure (SBP) at each follow-up time point will be computed as follows:

$$\text{SBP change from baseline} = (\text{SBP value at follow-up} - \text{SBP value at baseline})$$

7. Secondary patency rate at 9-months

Secondary patency rate at 9-months after a clinically-driven TLR which restores patency after total occlusion. For each subject-lesion, an indicator variable will be derived which identifies if the lesion meets secondary patency. The incidence of secondary of patency at 9 months will be computed as the number of subject-lesions that met secondary patency divided by the number of subject-lesions for the ITT population.

Confidential

8. Change in number and dosage of anti-hypertensive medications

Anti-hypertensive medications as well as the dosage will be recorded at baseline and throughout the study follow-up. The total number of anti-hypertensive medications will be computed as the sum of all available anti-hypertensive medications at each time point. Change from baseline will be computed as follows:

Change from baseline in the number of antihypertensive medications = (number of anti-hypertensive medications at follow-up – the number of anti-hypertensive medications at baseline)

Additionally, an indicator variable which detects if an increase in the number of antihypertensive medications (change from baseline > 0) was observed will be derived.

Similarly, the change from baseline in the anti-hypertensive medication dosage (within the same medication) will be computed as follows:

Change from baseline in the antihypertensive medication dosage = (Dosage of anti-hypertensive medication at follow-up – the dosage of the anti-hypertensive medication at baseline).

An indicator variable which identifies any increases in dosage (change from baseline > 0) will also be derived.

9. Renal function compared to baseline as measured by eGFR at 30-days and 9-months.

Renal function will be assessed by eGFR at the 30-days and 9-months of study follow-up. eGFR results will be estimated by the abbreviated Modification of Diet in Renal Disease(MDRD) equation : $186 \times (\text{Creat} / 88.4) - 1.154 \times (\text{Age}) - 0.203 \times (0.742 \text{ if female}) \times (1.210 \text{ if black})$.

The change from baseline in eGFR will be computed as follows:

Change from baseline in eGFR = (eGFR result at follow-up – eGFR result at baseline)

- i. In addition, an indicator variable will be derived in order to identify decreases from baseline in eGFR of >25%, >40%, >50% at any time point.

Amendment #1: 15Jul13

7.6.3.Safety Outcomes and Other Parameters

The main safety outcome is the incidence of subjects with any adverse event experienced after the study procedure has occurred over the totality of the study.

Other parameters collected to monitor safety and/or to derive efficacy include:

- Vital signs (systolic and diastolic blood pressure)
- Laboratory Assessments (chemistry, urine analysis, proteinuria, eGFR)
- Physical Examination (assessment of general appearance, abdomen, cardiovascular, dermatologic, genitourinary, head, eyes, ear, nose and throat (HEENT), lymph nodes, musculoskeletal, neurological, respiratory)
- Duplex Ultrasound (degree of stenosis)
- Angiography (degree of stenosis)
- Revascularization (number of revascularization, location, type)
- Concomitant medications/antihypertensive medications
- Mortality

8. STATISTICAL METHODS**8.1 General Statistical Considerations**

Data collected in this study will be presented using summary tables and subject data listings.

Demographic, endpoint information, safety data and other parameters will be summarized and presented for the ITT and Per-Protocol populations accordingly. Summaries for continuous and ordinal variables will include the number of observations (n), arithmetic mean, standard deviation (SD), minimum (min), maximum (max), median, and 95% confidence intervals of the means.

Minima and maxima will be reported with the same precision as the raw values; means, medians and quartiles will be presented to one additional decimal place than reported in the raw values.

Standard deviations will be presented to two additional decimal places than reported in the raw values.

For the time-to-event analysis, Kaplan-Meier (K-M) estimates at the indicated time points and K-M curve over time will be presented. In addition, K-M curves will be constructed for all time-to-

Amendment #1: 15Jul13

Confidential

event analysis using Kaplan-Meier methods. Confidence intervals (CI) will be at 95% confidence level (or applicable). All p-values will be rounded to four decimal places; p-values less than 0.0001 will be presented as “<0.0001”; p-values greater than 0.9999 will be presented as “>0.9999”.

Summaries for discrete variables will include frequency counts and percentages. All percentages will be rounded to one decimal place (i.e., XX.X%). Two-sided 95% exact confidence intervals will be displayed.

Change from baseline summaries will use the procedure visit (Day 0) as the baseline measure. For measurements that have a missing value at baseline, the data prior to the procedure visit (Day 0) will be used as the baseline measurement.

In addition, the primary endpoint rate and its one-sided exact 95% CI will be presented for subgroups (refer to section 8.9.4).

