## **2.3 SECONDARY ENDPOINTS**

The secondary endpoints will provide:

1. The occurrence of procedure-related MAEs reported as percentage of subjects with MAE, at 30-days, 9-months, 12-months, 24-months, and 36-months.  
Inclusive of:
  - a. Procedure-or device-related occurrence of death
  - b. Q-Wave MI
  - c. Clinically driven TLR
  - d. Significant embolic events
    - i. Defined as unanticipated kidney/bowel infarct clinically driven by symptoms of abdominal or back pain and confirmed with CT scan or open surgery, lower extremity ulceration or gangrene, or kidney failure after 30-days, 9-months, 12-months, 24-months, and 36-months.
2. Technical success defined as successful delivery and deployment of the iCAST™ RX Stent System with  $\leq 30\%$  residual angiographic stenosis after covered stent deployment (including post-dilatation) assessed via QVA by an independent core laboratory.
3. Procedural success defined as technical success without the occurrence of MAE prior to hospital discharge.
4. TLR measured as the proportion of subjects that require a clinically-driven reintervention of the target lesion through 9-months.
  - a. A clinically-driven TLR is defined as a TLR (PTA, bare metal stent or repeat covered stent deployment, or surgical bypass) due to documented recurrent hypertension from 30-days post-procedure level and/or deterioration in renal function from baseline value, associated with angiographic core laboratory adjudication of a  $\geq 60\%$  diameter covered stent restenosis.
5. Rate of incidental TLR defined as rate of TLRs not meeting the definition of a

clinically driven TLR.

6. Improved SBP control assessed at 30-days, 9-months, 12-months, 24-months and 36-months.
7. Secondary patency rate at 9-months after a clinically-driven TLR which restores patency after total occlusion.
8. Change in number and dosage of anti-hypertensive medications as compared to baseline.
9. Renal function compared to baseline as measured by eGFR at 30-days and 9-months.

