**Table 4: Derivation of TLR Performance Goal**

Author	# subjects	f/u time	TLR Assessment	Subjects with TLR	TLR
Rocha -Singh et al 	208	9 mo	9 mo	9	4.3%
Laird et al 	188	9-12 mo	9 mo	17	9.0%
Corriere et al 	91	12 mo	6 mo	10	11.0%
Rocha-Singh et al 	100	9 mo	9 mo	8	8.0%
Nolan et al 	78	12 mo	12 mo	8	10.3%
Nolan et al 	82	12 mo	12 mo	8	9.8%
Sapoval et al 	52	6 mo	6 mo	4	7.7%
Symonides et al 	27	6 mo	6 mo	8	29.6%
Van de Ven et al 	42	6 mo	6 mo	0	0.0%
Hennequin et al 	21	12 mo	9 mo	4	5.3%
			Weighted Average		8.5%

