6. CHANGES IN THE CONDUCT OF THE STUDY OR PLANNED ANALYSES

6.1 Changes in the Conduct of the Study

The enrollment for Protocol/CIP No. iCAST™ RX-ARAS-001 has been terminated after 68 subjects were screened and enrolled in the study as of November 2017. Enrolled subjects will be followed up to study completion.

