8.8 Unit of Analysis

For the primary functional endpoint of primary patency rate the unit of analysis is the atherosclerotic lesion(s). The rationale for analyzing the primary endpoint following a per lesion approach, is to avoid overestimation of the failure rate, as more lesions would be at risk for restenosis but would not be accounted for in a per subject analysis.

Since blood pressure is measured on the subject level, the primary clinical endpoint of change SBP will be evaluated at the subject level.

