9.10.1. TLR

The secondary endpoint of clinically driven TLR will be summarized using counts and frequencies. An exact binomial one-sided 95% confidence interval will be constructed and the upper limit compared to the Performance Goal rate of 8.5%. A p-value for the one-sided test of the difference between the observed rate and the Performance Goal will be presented.

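### The SAP counts clinically driven TLR per lesion, but the endpoint definition and the 8.5% goal are per subject, so the planned comparison mixes units

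*SAP*

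**What the plan says.** The protocol (2.3, item 4) defines the endpoint as "TLR measured as the proportion of subjects that require a clinically-driven reintervention of the target lesion through 9-months". The SAP repeats this in section 4, item 4: "To evaluate TLR measured as the proportion of subjects that require a clinically-driven re-intervention of the target lesion through 9-months".

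SAP 7.6.2 item 4, which gives the computing formula, says the percentage is "derived as the number of subject-lesions that require a clinically-driven re-intervention divided by the number of subject-lesions in the ITT population". It does not repeat the 9-month limit.

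SAP 9.10.1 then plans an exact binomial one-sided 95% interval, with the "upper limit compared to the Performance Goal rate of 8.5" percent, and a one-sided p-value. It names no unit. The goal comes from protocol Table 4, whose event column is headed "Subjects with TLR" and whose denominator is the number of subjects.

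Three other places bear on the unit:

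- SAP 8.8 assigns the lesion to primary patency and the subject to systolic blood pressure. It does not mention TLR.
- SAP 7.6.2 item 1 counts major adverse events, which include clinically driven TLR, by subject: "The incidence of MAE occurrence will be computed as the number of subjects with a reported MAE divided by the number of subjects".
- SAP sections 2 and 6.2 list the departures from the protocol. A new unit for TLR is not among them.

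**The concern.** Protocol 3.2 allows both renal arteries to be stented, so there can be more lesions than subjects. If each affected subject has one re-treated lesion, moving to lesions leaves the numerator unchanged and enlarges the denominator. The rate and its upper limit fall, and the comparison with a per-subject goal becomes easier for the device. A bilateral subject with both lesions re-treated works the other way. The exact binomial limit also treats two lesions in one subject as independent.

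The plan's own reason for analysing patency per lesion is to match the historical data (protocol 2.1, SAP 5.2). By that reasoning TLR should be per subject, because its historical data are. As written, one TLR event would also be reported on two denominators: lesions for TLR and subjects for major adverse events.

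TLR was the first of two secondary endpoints in the protocol's testing hierarchy (5.3.4), so readers are likely to look for this comparison.

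**Working it through.** **1. Reproduce the 8.5% goal.** Inputs: the ten rows of protocol Table 4, in order.

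- Subjects: 208 + 188 + 91 + 100 + 78 + 82 + 52 + 27 + 42 + 21 = 889
- Subjects with TLR: 9 + 17 + 10 + 8 + 8 + 8 + 4 + 8 + 0 + 4 = 76
- Pooled rate: 76/889 = 8.55%, printed as 8.5%

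The alternatives do not give 8.5%. The printed percentages weighted by subjects give 8.2%, and their simple mean is 9.5%. The 76 events over the Table 3 arteries for the same ten cohorts give 76/1006 = 7.6%, assuming one artery per event. The goal is therefore a per-subject rate.

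**2. Choose lesion counts.** SAP 6.1 says enrollment "has been terminated after 68 subjects were screened and enrolled in the study as of November 2017". The documents do not give the trial's lesion count, so two ratios are assumed:

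- 1.2 lesions per subject, the figure protocol 2.1 quotes from another trial: 68 × 1.2 = 81.6, taken as 82
- 1006/889 = 1.13, from Table 3: 68 × 1006/889 = 76.9, taken as 77

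**3. Apply the SAP 9.10.1 rule.** The one-sided 95% Clopper-Pearson upper limit for x events in n units is the 0.95 quantile of Beta(x+1, n−x). The exact p-value is P(X ≤ x) for X ~ Binomial(n, 0.085).

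| Events / units | Rate | Upper limit | p vs 8.5% | Below 8.5%? |
|---|---|---|---|---|
| 1/68 subjects | 1.5% | 6.79% | 0.017 | yes |
| 2/68 subjects | 2.9% | 8.97% | 0.064 | no |
| 2/72 lesions | 2.8% | 8.49% | 0.050 | yes |
| 2/77 lesions | 2.6% | 7.95% | 0.036 | yes |
| 2/82 lesions | 2.4% | 7.48% | 0.026 | yes |
| 3/82 lesions | 3.7% | 9.18% | 0.074 | no |
| 3/89 lesions | 3.4% | 8.48% | 0.049 | yes |

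Per subject, at most 1 TLR meets the goal. Per lesion, 2 meet it at any total from 72 to 88, and 3 from 89.

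**4. Chance of meeting the goal when the true subject rate is 8.5%.** Assume 68 subjects and 82 lesions (54 unilateral and 14 bilateral subjects; 54 + 2 × 14 = 82).

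- Per subject: P(X ≤ 1 | 68, 0.085) = 1.7%
- Per lesion, one re-treated lesion per affected subject: P(X ≤ 2 | 68, 0.085) = 6.4%
- Per lesion, both lesions of a bilateral subject always failing together: P(at most 2 lesions with TLR) = 4.7%

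**5. The opposite direction.** One bilateral subject with both lesions re-treated is 1/68 = 1.5% per subject but 2/82 = 2.4% per lesion. Both meet the goal. The result reverses against the device only at 69 to 71 lesions, where 1/68 passes and 2 lesions do not.

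**6. The last row of Table 4.** It prints 5.3% beside 4 of 21 subjects, and 4/21 = 19.0%. The 8.5% average uses the count of 4. If 5.3% is the correct entry, the pooled rate is 8.2% (1 of 21: 73/889 = 8.21%) or 8.1% (4 of 75: 76/943 = 8.06%). Against either figure the largest passing counts are unchanged: 1 of 68, 2 of 77 and 2 of 82.

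**The case against.** The strongest reply is that little hangs on this. SAP sections 2, 6.2, 8.7 and 9.10 make all inference descriptive and drop the hierarchy and type I error control, so no success claim rests on TLR. This stands and limits the severity. It does not remove the problem, because the SAP still plans the limit, the comparison with 8.5% and a p-value, and a descriptive comparison must also compare like with like.

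Other points on that side:

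- **SAP 9.10.1 names no unit.** That the comparison uses lesions is an inference. It is the natural one, because 7.6.2 holds the only computing formula. At best the SAP gives two definitions and leaves the choice open.
- **The flip is a one-event effect.** It needs exactly 2 TLRs, in different subjects, and 72 to 88 lesions. This is correct, and the lesion count is assumed.
- **The flip depends on the 95% limit.** At the 0.025 level that protocol 5.1 sets for the primary endpoints, 2/77 (p = 0.036) and 2/82 (p = 0.0256) both miss, and 2 TLRs pass only from 83 lesions. But both the protocol (5.3.6.2.1.1) and SAP 9.10.1 prescribe a one-sided 95% limit for TLR.
- **Inflation above 5% is not established.** This stands: of the two per-lesion figures, 6.4% is above 5% and 4.7% is below it. Both exceed the per-subject 1.7%.
- **An ITT denominator counts subjects lost before 9 months as free of TLR.** With 10% attrition assumed (61 of 68), 1/61 gives p = 0.030 against 0.017 for 1/68. This is true, but it applies equally to the present per-lesion ITT denominator and is a separate matter.
- **The Table 4 row is a side issue.** Agreed. It does not affect the unit finding.

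**Conclusion.** The concern holds. The computing formula in SAP 7.6.2 contradicts the endpoint definition in protocol 2.3 and SAP section 4, and it does not match the per-subject data behind the 8.5% goal. The change is not declared.

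The size is one event at the enrolled sample: the largest count that meets the goal is 1 per subject and 2 per lesion, for any total of 72 to 88 lesions. That range covers both assumed ratios, 1.13 and 1.2 lesions per subject. The per-lesion count usually favours the device but not always. Because the SAP treats inference as descriptive, the consequence is a misleading rate, limit and p-value set beside the goal. It should be corrected, but it does not undermine a confirmatory conclusion.

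**What to change.** - **SAP 7.6.2 item 4:** define TLR as the number of ITT subjects with at least one clinically driven TLR through 9 months, divided by the number of ITT subjects.
- **SAP 8.8 and 9.10.1:** state that the subject is the unit for TLR, and that only the per-subject rate, its limit and its p-value are compared with 8.5%. Report the per-lesion rate descriptively, without the goal.
- **Protocol Table 4, last row:** check it against its source. If 4 of 21 is right, 8.5% stands and only the printed percentage needs correcting. If 5.3% is right, note the pooled 8.1–8.2% beside the result and leave the pre-specified 8.5% unchanged.

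The cost is wording in three SAP sections and one literature check. No new data are needed. The per-subject comparison will usually be slightly stricter for the device.
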